**CONFIDENTIAL**

Date: 17 December 2020  
 Version: 4.0  
 Status: Final  
 Page: 95 of 110

**Novo Nordisk**

- Severe, moderate and mild TEAEs
- TEAEs with preferred term that are experienced by at least 5% of the subjects in any treatment or by at least 5% of all subjects

Summary tables of all SAEs including non-treatment emergent SAEs will be presented including summary tables based on system organ class and preferred terms.

### **Adverse events during the in-trial period, the pre-pregnancy period and the post-pregnancy period**

Adverse events with onset in the pre-pregnancy period, the post-pregnancy period as well as all AEs during the in-trial period will be summarised as described above for AEs with onset in the pregnancy period

#### **17.4.2.3 Pregnancy outcome endpoints**

##### **Supportive continuous and binary pregnancy outcome endpoints**

- Birth weight
  - Birth weight (kg)
  - Birth weight SD-score
  - Live born infants with birth weight < 10th percentile for gestational age and sex (local references) (yes/no)
  - Live born infants with birth weight > 90th percentile for gestational age and sex (local references) (yes/no)
- Pre-term delivery (delivery < 37 completed GWs) (yes/no)
- Early foetal death (delivery < 20 completed GWs) (yes/no)
- Perinatal mortality (death of foetus/infant between  $\geq 20$  completed GWs before delivery and < 1 completed week after delivery) (yes/no)
- Neonatal mortality (death of infant between  $\geq 7$  completed days after delivery and < 28 completed days after delivery) (yes/no)
- Presence of major abnormalities (classified according to EUROCAT) (yes/no)
- Neonatal hypoglycaemic episodes defined as plasma glucose  $\leq 1.7$  mmol/L (31 mg/dL) during the first 24 hours after birth or  $\leq 2.5$  mmol/L (45 mg/dL) between 24 hours and 48 hours after birth (yes/no)

The endpoints will be summarised by treatment arm for all infants and further sub-divided in the following groups:

- Mother randomised as pregnant
- Mother randomised as pregnant and exposed to trial drug at some point during the pregnancy period
- Mother randomised as pregnant and not exposed to trial drug at some point during the pregnancy period

Protocol  
Trial ID: NN1250-4300  
UTN: U1111-1191-3018  
EudraCT no.: 2017-000048-17

~~CONFIDENTIAL~~

Date: 17 December 2020  
Version: 4.0  
Status: Final  
Page: 96 of 110

**Novo Nordisk**

- Mother randomised as non-pregnant
- Mother randomised as non-pregnant and exposed to trial drug at some point during the pregnancy period
- Mother randomised as non-pregnant and not exposed to trial drug at any point during the pregnancy period

The classification of congenital anomalies will be listed.

#### **Adverse events in the infant from delivery to final follow-up**

Adverse events will be coded using the most recent version of the MedDRA database.

Adverse events are summarised descriptively for all infants and additionally sub-divided in the following groups:

- Mother randomised as pregnant
- Mother randomised as pregnant and exposed to trial drug at some point during the pregnancy period
- Mother randomised as pregnant and not exposed to trial drug at some point during the pregnancy period
- Mother randomised as non-pregnant
- Mother randomised as non-pregnant and exposed to trial drug at some point during the pregnancy period
- Mother randomised as non-pregnant and not exposed to trial drug at any point during the pregnancy period

The summaries will display the number of infants with at least one event (N), the percentage of infants with at least one event (%) and the number of events (E). Summaries will be presented as an overview including all AEs, serious AEs, AEs by severity and AEs by relation to treatment.

Furthermore, summary tables based on system organ class and preferred terms are made for:

- All AEs
- SAEs
- AEs possibly or probably related to trial product
- Severe, moderate and mild AEs
- AEs with preferred term that are experienced by at least 5% of the infants in any treatment or by at least 5% of all infants

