### Missing data considerations – primary estimand

When estimating the primary estimand, missing data will mainly be due to withdrawal from the trial. In the trials NN1250-3770, NN1250-3583 and NN1250-3585 (all with IDeg as IMP and parallel trial design) with a duration of 26-52 weeks in subjects with T1DM, the proportion of withdrawn subjects varied between 8% and 16%. In these trials subjects were withdrawn if they discontinued trial drug and did not attend any scheduled visits after discontinuation.

For subjects randomised as non-pregnant, the trial may potentially be of close to 2 years duration, suggesting higher drop-out rates than observed in the above mentioned trials. However, pregnant women and women with the intention to become pregnant are likely more adherent than subjects with diabetes in general. It is assumed that at most 15% of the women randomised as non-pregnant and 10% of the women randomised as pregnant will discontinue treatment. It is expected that approximately 80% of the pregnant women will be randomised as pregnant, and that in total, the percentage of subjects discontinuing treatment is smaller than 12%. Provided it is possible to retrieve data from half of these subjects, 6% of the subjects may have missing data due to withdrawal from the trial.

Within each treatment arm, missing data at the last planned visit prior to delivery after GW 16 from subjects who have discontinued treatment will be imputed from the distribution of retrieved data at the last planned visit prior to delivery after GW 16 among subjects who have discontinued treatment. Missing data at the last planned visit prior to delivery after GW 16 from subjects who have not discontinued treatment will be imputed based on the distribution among subjects who have not discontinued treatment at the last planned visit prior to delivery after GW 16. If a simple intercept model is infeasible to estimate among discontinued subjects, an on-treatment factor will be included in the model instead of doing the imputation separately by on-treatment and off-treatment. A detailed description of the imputation procedure is described in Section [17.3.1](#).

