## 18.2 Informed consent

In seeking and documenting informed consent, the investigator must comply with applicable regulatory requirement(s) and adhere to ICH GCP and the requirements in the Declaration of Helsinki.

Before any trial-related activity, the investigator must give the subject verbal and written information about the trial and the procedures involved in a form that the subject can read and understand.

The subject must be fully informed of their rights and responsibilities while participating in the trial as well as possible disadvantages of being treated with the trial products.

If required by local legislation, the father of the foetus (if known) must be asked to sign an agreement form before delivery in order to collect blood samples as well as health information about the infant after delivery. If the father of the foetus is not known this must be documented in the subject's medical records. If the father of the foetus refuses to give his consent, this information will not be collected.

The investigator must ensure the subject ample time to come to a decision whether or not to participate in the trial.

A voluntary, signed and personally dated informed consent must be obtained from the subject before any trial-related activity.

The responsibility for seeking informed consent must remain with the investigator, but the investigator may delegate the task to a medically qualified person, in accordance with local

Protocol  
Trial ID: NN1250-4300  
UTN: U1111-1191-3018  
EudraCT no.: 2017-000048-17

CONFIDENTIAL

Date: 17 December 2020  
Version: 4.0  
Status: Final  
Page: 99 of 110

Novo Nordisk

requirements. The written informed consent must be signed and personally dated by the person who seeks the informed consent before any trial-related activity.

If information becomes available that may be relevant to the subject's willingness to continue participating in the trial, the investigator must inform the subject in a timely manner, and a revised written subject information must be provided and a new informed consent must be obtained.

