**Table 4–2 Overview of defined analysis sets**

Defined Analysis Set	Description
Full analysis set for pregnant women (FASpregnant)	Includes all randomised women who are pregnant during the trial. Subjects in the FAS pregnant will contribute to the evaluation “as randomised”.
Per protocol analysis set for pregnant women (PPpregnant)	Includes subjects from FAS pregnant who: 
 
• Have not violated any inclusion criteria
 
• Have not fulfilled any exclusion criteria
 
• Are exposed to trial drug at least the first four weeks after randomisation or, in case of termination of pregnancy within the first four weeks after randomisation, until time of termination of pregnancy.
 
 Subjects in the PP pregnant analysis set will contribute to the analysis according to the treatment received prior to potential discontinuation of randomised treatment. This will be referred to as contributing to the evaluation “as treated”.
Safety analysis set for pregnant women (SASpregnant)	Includes all randomised women exposed to at least one dose of trial product and who are pregnant during the trial. Subjects in the SAS pregnant will contribute to the evaluation “as treated”.

The primary endpoint and secondary efficacy endpoints are analysed using full analysis set for all pregnant women.

Statistical Analysis Plan  
 Trial ID: NN1250-4300  
 UTN: U1111-1191-3018  
 EudraCT No: 2017-000048-17

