**Novo Nordisk**

The endpoints will be summarised by treatment arm for all infants and further sub-divided in the following groups:

- Mother randomised as pregnant
- Mother randomised as pregnant and exposed to trial drug at some point during the pregnancy period
- Mother randomised as pregnant and not exposed to trial drug at any point during the pregnancy period
- Mother randomised as non-pregnant
- Mother randomised as non-pregnant and exposed to trial drug at some point during the pregnancy period
- Mother randomised as non-pregnant and not exposed to trial drug at any point during the pregnancy period

For the above mentioned endpoints summary statistics will be provided. Instead of summarising only as (yes/no) categories some endpoints will be categorised into (yes/no/Unaddressed) categories where 'Unaddressed' refer to cases where the parents did not consent to share information after delivery or did not complete the pregnancy outcome form and to withdrawn subjects who did not give any further information.

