#### **Adverse events in the infants from delivery to final follow-up**

This endpoint will be summarised for infants related to safety analysis set for pregnant women.

It is unknown whether adverse events on the day of delivery occurred before or after the actual delivery, as exact times were not collected. Adverse events and deliveries on either side of midnight could also be coherent. Therefore, adverse events from 1 calendar day before delivery to final follow-up are included.

Adverse events will be coded using the most recent version of the MedDRA database.

Adverse events will be summarised descriptively for all infants and additionally sub-divided in the following groups:

- Mother randomised as pregnant
- Mother randomised as pregnant and exposed to trial drug at some point during the pregnancy period

Statistical Analysis Plan  
Trial ID: NN1250-4300  
UTN: U1111-1191-3018  
EudraCT No: 2017-000048-17

~~CONFIDENTIAL~~

Date: 27 January 2021  
Version: 2.0  
Status: Final  
Page: 29 of 34

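### Infant adverse-event percentages have no category for delivered infants without post-delivery information, so as the plan reads these infants count as event-free

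*Protocol*

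**What the plan says.** **Who is summarised.** Protocol 17.4.2.3, under the infant AE heading, says: "Adverse events are summarised descriptively for all infants and additionally sub-divided in the following groups". SAP 5.4.3 has the same population, "Adverse events will be summarised descriptively for all infants and additionally sub-divided in the following groups", and adds: "This endpoint will be summarised for infants related to safety analysis set for pregnant women". SAP Table 4–2 defines that set by the mother alone: "Includes all randomised women exposed to at least one dose of trial product and who are pregnant during the trial". It sets no condition on infant follow-up.

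**What is shown.** "The summaries will display the number of infants with at least one event (N), the percentage of infants with at least one event", followed by the event count. The SAP display is the same.

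**Infants without information are foreseen.** Protocol 18.2 covers places where local law requires the father's agreement to collect infant data: "If the father of the foetus refuses to give his consent, this information will not be collected". SAP 5.4.3, just before its infant AE heading, gives some of the preceding yes/no outcomes a third category, 'Unaddressed'. It is said to "refer to cases where the parents did not consent to share information after delivery"; it also covers an uncompleted outcome form and a withdrawn mother who supplied nothing more. SAP Appendix 2 (6.2.2) repeats this. The endpoints that receive the category are not named, and neither place extends it to infant AEs.

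**The concern.** An AE summary records only events that were reported, so in the data an infant nobody could follow looks the same as an infant who stayed well. If both sit in the denominator, the AE and serious AE (SAE) percentages are too low. The same infant could be 'Unaddressed' for neonatal hypoglycaemia and, in the next set of tables, count as having had no AE.

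Infant AEs are a named supportive endpoint for the pregnancy-outcome objective, and Protocol 3.1 notes that degludec had not been tested in a clinical trial with pregnant subjects. Allocation is open-label, so the share of infants without information could differ by arm, and that alone would shift the between-arm comparison.

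**Working it through.** The documents state no figure for this point, so there is nothing to reproduce. The check is how far an all-infant denominator moves the percentage.

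**Inputs**
- p, the risk of at least one AE among infants with information: not in the documents; assumed 20–50%.
- u, the share of delivered infants without information who stay in the denominator: not in the documents. The nearest figure is in Protocol 17, missing data for the primary estimand: "6% of the subjects may have missing data due to withdrawal from the trial". It is half of an upper bound of 12% discontinuing treatment (0.5 × 12% = 6%) and concerns HbA1c. It serves here only as a proxy, with 12% as a higher case.
- Arm size: SAP 6.3.1.1 gives 188 women in the full analysis set for pregnant women. An even split and one infant each, both assumptions, give 188/2 = 94 infants per arm.

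**Step 1. Size of the understatement.** Reported % = p(1 − u); shortfall = p × u.

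| p | Reported, u = 6% | Shortfall (points) | Reported, u = 12% | Shortfall (points) |
|---|---|---|---|---|
| 20% | 18.8% | 1.2 | 17.6% | 2.4 |
| 30% | 28.2% | 1.8 | 26.4% | 3.6 |
| 40% | 37.6% | 2.4 | 35.2% | 4.8 |
| 50% | 47.0% | 3.0 | 44.0% | 6.0 |

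**Step 2. In counts.** 94 × 0.06 = 5.64, so take 6 infants without information, and suppose 28 have an AE. Over all infants: 28/94 = 29.8%. Over infants with information: 28/(94 − 6) = 28/88 = 31.8%.

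**Step 3. Unequal shares, equal true risk.** Spurious difference = p(u₂ − u₁).
- 0% against 6%: 1.2–3.0 points for p = 20–50%.
- 0% against 12%: 2.4–6.0 points.
- 3% against 9% at p = 40%: 38.8% against 36.4%, a difference of 2.4 points.

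**Step 4. Against sampling error.** With 94 infants per arm and p = 40%, the 95% half-width for the difference is 1.96 × √(2 × 0.4 × 0.6/94) ≈ 0.14, or about 14 points.

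**The case against.** **The denominator is inferred.** A reader might take the plan to instruct that unobserved infants be counted as event-free. Neither document says so; it is the arithmetical result of summarising all infants with no exclusion. The Protocol text does not mention the safety set, which comes from the SAP. The Protocol Glossary counts an infant from delivery, and SAP 5.4.3 speaks of infants or foetuses for the outcome endpoints but only of infants for AEs. A woman lost while pregnant may therefore contribute no infant at all. This stands, and limits the point to infants known to have been delivered.

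**Withdrawal does not mean an unobserved infant.** Protocol 8.3.4, 8.4.5 and 12.5 ask for outcome and infant-health information on paper forms after withdrawal, and 18.3 keeps data already collected. Paternal refusal matters only where local law requires the agreement. This stands too, although retrieval is an effort and will not always succeed.

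**The 6% is not a rate of missing infants.** A reader might infer a demonstrated bias of that order. The figure was planned for HbA1c and does not support this.

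**Missing time denominator.** A reader might see a defect in giving mothers, but not infants, a rate per 100 years of exposure. Planned infant follow-up is nearly uniform: 28 days to end of treatment and 30 more to V92, 58 in all (Protocol 8.4.3, 8.5.3). A woman's time in the trial varies, up to 25 months. The omission is a matter of preference.

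**Descriptive analysis, partly visible.** No test is planned, sampling error is much larger than the artefact, and the 'Unaddressed' counts for other endpoints show part of the problem. This limits the consequence. It does not tell the reader what the AE percentage is based on.

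**Conclusion.** The point holds as a minor weakness in a descriptive summary. Under the plain reading of the denominator, the direction is certain: any delivered infant without information lowers the AE and SAE percentages, and unequal shares distort the comparison of arms. The size is unknown. At the 6% proxy it is about 1–3 points for p = 20–50%, with p and u both assumed; the documents do not establish that a bias of this size will occur.

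The percentage over infants with information is not free of assumptions either. It represents all infants only if the unobserved ones had a similar risk. That is a reason to show both percentages with the counts behind them.

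**What to change.** In SAP 5.4.3, under the infant AE heading:

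1. Show by arm the number of infants without post-delivery information, using the existing 'Unaddressed' reasons.
2. Show by arm the number whose follow-up ended before V92.
3. Give AE and SAE percentages over infants with any post-delivery information or any recorded AE, beside the all-infant percentages.

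The denominator in item 3 should not be narrowed to live-born, assessed infants. The SAP counts events from one calendar day before delivery, so a narrower base could keep an event in the numerator while dropping its subject from the denominator. A rate per infant-years is not needed.

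The cost is one extra row and one extra column in descriptive tables, and slightly higher percentages in the added column. No new data are required. Events missing from the event count for unobserved infants cannot be recovered by any change of denominator.

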#### **17.5 Exploratory endpoints and other assessments**

The exploratory endpoints listed in Section [4.5](#) and other assessments listed in Section [4.6](#) will be presented using summary statistics.

Protocol  
 Trial ID: NN1250-4300  
 UTN: U1111-1191-3018  
 EudraCT no.: 2017-000048-17

**CONFIDENTIAL**

Date: 17 December 2020  
 Version: 4.0  
 Status: Final  
 Page: 97 of 110

**Novo Nordisk**

## 18 Ethics

### 18.1 Benefit-risk assessment of the trial

The trial population consists of pregnant subjects with T1DM. For this population a good glycaemic control without experiencing hypoglycaemia is of great importance in order to minimise the risk for complications during pregnancy and for the pregnancy outcome. The same ethical principles apply to trials in pregnancy as in all other trials, however special attention must be given to the particular situation carrying and having a child. Consideration must be given to the emotional state of the mother in relation to the infant or the pregnancy with regard to the trial requirements. For all subjects participating in this trial, the anticipated benefits include a very close follow-up during their pregnancy potentially resulting in improved glycaemic control. Titration algorithms specifying recommended adjustments of the basal insulin dose at different plasma glucose levels are used in order to ensure subjects receive an optimal treatment. Subjects will receive intensive medical care by means of close contact to the clinical sites with at least weekly contacts.

Trial products will be provided by Novo Nordisk free of charge. Subjects will be provided with a BG-meter including lancets, plasma-calibrated test strips and control solutions as well as instructions for use. Subjects will receive IDeg and IAsp or IDet and IAsp in prefilled pens. For a description of risks and benefits please refer to current versions and any updates of the IDeg IB, the SmPC for IDeg, IDet and IAsp and/or local approved product information, if applicable.

Currently only IDet and IAsp are approved for use by pregnant subjects with T1DM. For many clinicians the use of IDeg during pregnancy seems a compelling choice as basal insulin due to its low variability and low risk of hypoglycaemia. There is no information available today indicating any other risks in connection with the use of IDeg, neither for the pregnant women nor for the foetus, than those found with IDet. The trial products may be associated with side effects, but relevant precautions have been implemented in the design and planned conduct of the trial in order to minimise the risks and inconveniences of participating in the trial. These precautions include thorough information regarding the correct administration of the trial product and handling of low BG measurements. Furthermore, subjects will be fully informed about possible AEs and inconveniences before initiation of any trial related activities.

#### **Clinical benefits and risk considerations for the trial**

For the individual subjects, the personal health-related benefits are related to the medical examination and the benefit from a treatment regimen anticipated being equal to or better than the treatment they receive at the time they enter the trial. However, subjects will have to spend some extra time monitoring and recording data and on additional visits to the clinic and phone contacts.

Protocol  
Trial ID: NN1250-4300  
UTN: U1111-1191-3018  
EudraCT no.: 2017-000048-17

CONFIDENTIAL

Date: 17 December 2020  
Version: 4.0  
Status: Final  
Page: 98 of 110

Novo Nordisk

The high frequency of contacts between the subject and the investigator and the thorough evaluation of SMPG values will provide the opportunity for optimising the titration of basal and bolus insulin and thereby may contribute to obtaining improved HbA1c results.

For the individual subjects, the anticipated side effects associated with the trial products are not different from what is seen with other insulins and include hypoglycaemia, hypersensitivity reactions, injection site reactions and lipodystrophy. The side effects will be mitigated by the close supervision of the subjects, the frequent measurements of BG levels and the review and monitoring of data by the DMC. Detailed information about trial products is available in the current edition and any updates of the IDeg IB, the SmPC for IDeg, IDet and IAsp and/or local approved product information, if applicable.

Subjects in this trial will benefit from a basal-bolus insulin treatment in a TTT setting under close supervision. It is concluded that the clinical benefits from the trial outweigh the potential risks of participating in this trial.

